8.3 Assessment of DOAC Dipstick by DOASENSE Reader

Measurement

After the urine strip has been immersed in the urine sample for approx. 2-3 seconds according to the instructions for use, the strip is placed on the strip holder of the DOASENSE Reader after 10 minutes and the START button is pressed. The device pulls the strip holder and carries out the measurement. The result of the four pads is displayed on the screen and printed on the thermal printer. After measuring the strip, the device ejects the strip holder. The strip is removed and disposed of.

The output of DOASENSE Reader are 3-digit values reprinting the %REM values (reflectance units) of the 4 pads and printed by the Reader of the printer for each measurement that is attached with an adhesive by the study personal into the CRF. These values are then written with a ball point pen on the right part of the printed values because the printout may lose color over time.

8.4 Analysis by LC-MS/MS

Urine samples will be analyzed at Laboratory Limbach by LC-MS/MS. The method is described elsewhere (23). The results are given as ng/ml. Normal range of values is 0.1 to 4.0 ng/ml (23). Normal values are interpreted as “negative”. Higher values represent “positive” results. Optionally, the upper limit of normal range may be changed to 8 ng/ml if values between 4 ng/ml and 8 ng/ml occur in more than 0.5% of patients.

Methodological reasons may lead to a repeated measurement of the urine sample diluted 1:15. Analyses will be repeated with this dilution if concentration of DOAC in urine is > 50.000 ng/ml or is expected to be above this value. The repetition is required to ensure that the concentration is in the linear range of detection range of LC-MS/MS. However, the dilution affects the normal range, which is 15-fold higher compared to samples that are

Confidentiality Statement

This document is confidential and proprietary to Sponsor and HLZ Medizinische Statistik and for restricted circulation and access only. No part of it may be transmitted, reproduced, published or used by any person/s without prior written authorization.

analysed without this dilution. For the statistical evaluation these mean of the normal range without dilution will be used.

Remark: The personal at Limbach laboratory is blinded regarding the information which DOAC the patient is taken. The personal does not have access to any information in the CRF which DAOC the patient was taking.

8.5 Analysis of Creatinine in urine

Creatinine is determined in urine by the method of Jaffe et al at Laboratory Limbach (24). Normal values are below 0.25 g/l. Values below 0.25 g/l are interpreted as "low" and higher values are interpreted as "normal". The normal range of creatinine may change upon the results of the measurement because reduced renal function with low creatinine is a contraindication for the therapy with a DOAC. If a diagnosis of renal insufficiency is documented in a patient, low creatinine value has to be interpreted as correct low. However, changes may be required upon the results of the determination of creatinine by laboratory Limbach. These decisions are made by the Steering Committee.

Data are transferred unchanged by software to an Excel file at Laboratory Limbach. This file is stored on a password secured USB flash drive and brought to the Institute for Biometry and Statistics by the Co-ordinating Investigator. [name] imports the data from Excel to SAS. Treatment of patients and data of LC-MS/MS remain blinded during this procedure. Six months after termination of the analysis of DOACs by LC-MS/MS and creatinine by Jaffe Method urine samples are discarded. This period may be changed upon request of the Sponsor of the study.

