8.2 Visual assessment of colours of pads of DOAC Dipstick

Note: Site personnel with known red-green blindness/ weakness cannot perform the test.

The site personnel will perform the visual urine test as follows:

The test strip is dipped into urine or into control samples for 2 to 3 seconds, so all test pads are wet with urine. Then, the test strip is placed on a flat surface (room temperature, at light) with

Confidentiality Statement

This document is confidential and proprietary to Sponsor and HLZ Medizinische Statistik and for restricted circulation and access only. No part of it may be transmitted, reproduced, published or used by any person/s without prior written authorization.

the pads facing upwards (so color changes can be seen). After 10 Minutes the site personnel will compare the results visually with the reference scale on the dipstick container. Then, the dipstick will be placed into the reflectance photometric reader according to the handling instructions.

The study personnel will document the results in the CRF and the printout of the reflectance photometric color reader (DOASENSE Reader) will be copied and fixed with an adhesive into the CRF.

After 10 minutes, the reactions on the pads are completed. The colours of the pads are identified by naked eye of the study personnel and judged as follows by comparing the colour label attached to the test tube.

The text for the identification of the colour by the observer is taken form the instructions for use (annex 2) and as follows:

[figure not shown]
Test Pad 1: (Creatinine)

- The color of pad 1 corresponds to colors “norm.” on the tube label - creatinine in urine is normal. Pad 3 and pad 4 can be evaluated.
- The color of pad 1 is darker than the colors “norm.” on the tube label - high creatinine does not affect DOAC excretion into urine. Pad 3 and pad 4 can be evaluated.
- The color of pad 1 is “low” or lighter than the respective color of the tube label - creatinine in urine is low, indicating renal insufficiency.

Colors of pad 3 and pad 4 may be false negative.

Confidentiality Statement

This document is confidential and proprietary to Sponsor and HLZ Medizinische Statistik and for restricted circulation and access only. No part of it may be transmitted, reproduced, published or used by any person/s without prior written authorization.

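### SAP section 8.5 calls urine creatinine below 0.25 g/l both normal and low, lets the limit change after results are seen, and leaves the renal-diagnosis rule ambiguous

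*SAP*

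**What the plan says.** All of the following stands in SAP section 8.5, which defines the Jaffe creatinine reference.

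- Direction of normal: "Normal values are below 0.25 g/l".
- Classification, in the very next sentence: "Values below 0.25 g/l are interpreted as" low, and higher values are normal.
- Movable limit: "The normal range of creatinine may change upon the results of the measurement". The section repeats that changes may prove necessary once the laboratory results are in, and adds: "These decisions are made by the Steering Committee".
- Diagnosis rule: "If a diagnosis of renal insufficiency is documented in a patient, low creatinine value has to be interpreted as correct low".

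The reference is used in section 18, tables 12 and 13. These count correct and false low and normal Dipstick results against the Jaffe method in groups A and B. Section 10.2, item XI (numbered XII in section 9.2.2) compares quantitative Jaffe creatinine with the Reader's qualitative result and requires a creatinine cut-off to be determined.

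**The concern.** An accuracy table needs one fixed reference class per patient, set without regard to the test being judged. Section 8.5 falls short in three ways.

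1. Two adjacent sentences give opposite classes to the same value, and a value of exactly 0.25 g/l has none.
2. The limit may be redrawn after the results are available. The section gives no criterion. Its blinding statement covers treatment and LC-MS/MS data during data transfer, not pad-1 readings. If the limit is chosen with pad and Jaffe results both in view, the agreement reported is the best of several candidates.
3. The diagnosis rule brings in information from outside the assay and works in one direction. It can confirm a low value, but no counterpart exists for a normal value in a patient without the diagnosis.

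At stake is the credibility of the pad-1 accuracy figures in tables 12 and 13. A correct protocol would not cure the wording, because section 11 lets the SAP prevail where the two conflict.

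**Working it through.** The SAP states no creatinine accuracy, prevalence or sample-size figure, so there is none to reproduce. The check has three parts.

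**1. Which sentence is meant.** Three places bear on the direction:
- The second sentence of section 8.5 gives the only full rule: below 0.25 g/l low, higher normal.
- Section 8.2: when pad 1 matches the low colour or is lighter, "creatinine in urine is low, indicating renal insufficiency".
- Section 8.6: the negative control urine contains 1.5 g/L creatinine and the positive control contains none.

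Section 8.2 and the control urines fit the second sentence, and nothing else in the SAP supports the first.

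If the first sentence were nevertheless programmed, the reference labels would swap. Sensitivity would become 1 − specificity, specificity 1 − sensitivity, and accuracy 1 − accuracy. Assumed true values of 90%/95% would appear as 5%/10%, and 80%/90% as 10%/20%.

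**2. What the diagnosis rule does.** Two readings are possible.
- *Jaffe value meant:* a low Jaffe value is already low by the reference. Nothing is reclassified and there is no bias.
- *Pad value meant:* a pad-low, Jaffe-normal result in a patient with documented renal insufficiency moves to the correct-low cell.

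For the second reading, let TP, FN, TN and FP be the counts with Jaffe low as the target condition, f the share of FP with the diagnosis, and m = f × FP. Then:
- sensitivity′ = (TP + m) / (TP + m + FN)
- specificity′ = TN / (TN + FP − m)
- PPV′ = (TP + m) / (TP + FP)

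Assumptions not in the SAP: 3% or 10% of patients with low creatinine, true sensitivity/specificity of 90%/95% or 80%/90%, and f from 10% to 50%. For scale, section 6.2 gives 440 per group including 12% drop-out, so 2 × 440 × 0.88 = 774.4 evaluable. The proportions do not depend on this number.

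One case in full (3% low, 90%/95%, f = 50%):
- Low: 774.4 × 0.03 = 23.2, so TP = 20.9 and FN = 2.3.
- Normal: 751.2, so TN = 713.6 and FP = 37.6.
- m = 18.8.
- Sensitivity′ = 39.7/42.0 = 94.5%; specificity′ = 713.6/732.4 = 97.4%.
- PPV goes from 20.9/58.5 = 36% to 39.7/58.5 = 68%.

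All cases, with f from 10% to 50%:

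| Low creatinine | True sens./spec. | Sensitivity′ | Specificity′ | PPV, then PPV′ |
|---|---|---|---|---|
| 3% | 90%/95% | 91.4–94.5% | 95.5–97.4% | 36%, then 42–68% |
| 3% | 80%/90% | 84.9–92.4% | 90.9–94.7% | 20%, then 28–60% |
| 10% | 90%/95% | 90.4–91.8% | 95.5–97.4% | 67%, then 70–83% |
| 10% | 80%/90% | 81.7–86.2% | 90.9–94.7% | 47%, then 52–74% |

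Every shift favours the pad. The gain is 0.4 to 12.4 points in sensitivity and 0.5 to 4.7 points in specificity.

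**3. The movable limit.** The SAP gives no distribution of creatinine values, so this cannot be sized. The direction depends on what the Committee sees. The best agreement over several candidate limits is never below the agreement at a limit fixed beforehand. A choice made with pad results in view therefore tends to flatter the pad. A choice made on Jaffe values alone need not, but the limit would still not be prespecified.

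**The case against.** The strongest reply is that this is a drafting slip in a secondary analysis. The second sentence is explicit and sections 8.2 and 8.6 agree with it, so a competent programmer would use it. A reader might infer from the first sentence that pad-1 accuracy will come out inverted. The documents do not support that, since inversion requires literal use of a sentence that the rest of the SAP contradicts. This part of the reply stands.

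The reply also holds that the diagnosis rule sits in a section about the laboratory assay and never mentions the strip, so it may merely accept a low Jaffe value as genuine. A reader might infer that strip-low results in renal patients can never be errors. That follows only under the pad reading. The word *correct*, also used in tables 12 and 13, makes the pad reading plausible, and under the Jaffe reading the sentence does no work. Neither reading is certain. In addition, section 10.1.11 has patients found afterwards to have reduced renal function evaluated individually, and tables 12 and 13 are listed under the per-protocol analysis. Few such patients may be left in those tables.

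A third tempting inference is that a faulty reference distorts the warning that pads 3 and 4 may be falsely negative. It does not: section 8.2 ties that warning to the colour of pad 1, not to Jaffe. Section 10.2, item XII (Dipstick versus Reader) uses no Jaffe value, and the primary comparison is with LC-MS/MS.

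The reply does not answer the movable limit, the unclassified value of 0.25 g/l, or the need to say which value the diagnosis rule concerns.

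**Conclusion.** Wrong as written, with consequences confined to the secondary pad-1 versus Jaffe accuracy results in tables 12 and 13. The contradiction at 0.25 g/l and the unassigned boundary value are plain from the text. So is the permission to change the limit after results without a criterion. The diagnosis rule is ambiguous: under the pad reading it biases in the pad's favour only, and under the Jaffe reading it has no effect.

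The SAP supplies nothing from which to size the effect. The figures above are illustrations that rest on the assumed prevalence, accuracy and share of false lows with a renal diagnosis. They show direction and plausible order, not an expected result.

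**What to change.** In SAP section 8.5:

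1. Correct the first sentence to agree with the second (below 0.25 g/l low, otherwise normal), and state explicitly which class 0.25 g/l itself belongs to.
2. Fix this limit for tables 12 and 13 before pad and Jaffe results are compared. Report any later limit, including a cut-off derived under section 10.2, item XI, as a labelled exploratory or sensitivity result. Item XI can then still be carried out as planned.
3. State that the Jaffe value alone sets the reference class, and replace the diagnosis rule accordingly. Report pad-1 results by documented renal insufficiency as a separate description.

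The cost is SAP wording only. Pad-1 accuracy may look slightly less favourable than under the pad reading of the diagnosis rule.

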8.6 Assessment of DOASENSE Control Urines

At start of study, and after every 12th examination of patient urine samples, on a DOAC Dipsticks are analysed by the visual reading and by DOASENSE Reader using DOASENSE Control Urines that are a negative control (0 ng/mL Rivaroxaban and Dabigatran, 1.5 g/L

Confidentiality Statement

This document is confidential and proprietary to Sponsor and HLZ Medizinische Statistik and for restricted circulation and access only. No part of it may be transmitted, reproduced, published or used by any person/s without prior written authorization.

creatinine and normal urine colour) and a positive control (800 ng/mL Rivaroxaban and Dabigatran and no creatinine) as described above. The results are documented on a separate page of the CRF (Quality Control to be performed at start of Study, and after every 12th Examination of Patient Urine Samples (9.5.3. Page 21, Study Protocol)) (annex5) provided by DOASENSE.

8.7 Questionnaire on user handling of DOAC Dipstick

The aim of the content of the questionnaire is to gather information on the handling and the performance of DOAC Dipstick by the user. A questionnaire that contains statements on the handling of DOAC Dipstick and the colour scale has to be compiled by the study personnel who perform the testing with DOAC Dipstick after the analysis of the 5th and 15th patient (annex 6).

8.8 Clinical Efficacy and Safety Endpoints

This is a non-interventional study to determine the accuracy of the IVD DOAC Dipstick in comparison to the concentration of the analytes in spontaneously obtained urine sample of patients on chromic treatment with DOACs. Clinical endpoints are not part of the determination of the accuracy of DOAC Dipstick in the study.

The patients will not have additional risks due to participation in the investigation, and will not benefit directly by participating. Only patients who already take oral direct Factor Xa or Thrombin inhibitors will be included into the trial. They will provide a spontaneous urine sample for testing and will not come into contact with the test itself.

Therefore, clinical efficacy and safety endpoints are not defined for this study.

Confidentiality Statement

This document is confidential and proprietary to Sponsor and HLZ Medizinische Statistik and for restricted circulation and access only. No part of it may be transmitted, reproduced, published or used by any person/s without prior written authorization.

9. EFFICACY PARAMETERS

9.1 Primary Efficacy Endpoint

The primary efficacy endpoint is to assess the performance of the results for oral direct Factor Xa and Thrombin inhibitors of the **qualitative** visual analysis of the IVD **DOAC Dipstick** from urine samples of patients on treatment with DOACs in comparison with the **quantitative** results of DOACs obtained by **LC-MS/MS** quantification.

In case the cut-off values are different for apixaban, edoxaban and rivaroxaban, as determined by LC-MS/MS this has to be taken into account for the analysis. In such case LC-MS/MS may be transformed to qualitative data for the analysis of the primary endpoint.

9.2 Secondary Efficacy Endpoints

9.2.1 DOACs

- I. Comparison of the **qualitative DOAC Dipstick** results with the **qualitative** results of the **DOASENSE Reader** for DOACs
- II. Comparison of the **qualitative** results of the **DOAC Dipstick** with the **quantitative** results of **DOASENSE Reader**.
- III. Comparison of the **qualitative** results of the **DOASENSE Reader** with the **quantitative** results of **DOASENSE Reader**. Differences between readers have to be respected and if so, included into this analysis. Each center has an individual reader. Readers are standardized before delivery from the producer by adequate tastings, which, however do not include samples of patients under treatment. This has to be analyzed statistically in an adequate way. Number of samples may not be sufficient for all readers.
- IV. Determination of the inter-center reliability for centers including more than 30 patients
- V. Comparison of the **qualitative** results of the **DOASENSE Reader** with the **quantitative** results of **LC-MS/MS**. The results of Rivaroxaban, Apixaban and

Confidentiality Statement

This document is confidential and proprietary to Sponsor and HLZ Medizinische Statistik and for restricted circulation and access only. No part of it may be transmitted, reproduced, published or used by any person/s without prior written authorization.

Edoxaban have to be analyzed separately because of different concentration ranges during therapy by LC-MS/MS.

- VI. Comparison of the **quantitative** results of the **DOASENSE Reader** with the **quantitative** results of **LC-MS/MS** is performed. The results of Rivaroxaban, Apixaban and Edoxaban have to be analyzed separately because of different concentration ranges during therapy by LC-MS/MS.
- VII. Analysis of an **interaction of demographic data** on the results of **DOAC Dipstick, DOASENSE Reader and LC-MS/MS** (demographic data, creatinine)
- VIII. Analysis **dose, last intake and duration of treatment** with each DOAC on **qualitative** results of **DOAC Dipstick** and **DOASENSE Reader** and **quantitative** results of **LC-MS/MS**
- IX. Analysis of an **interaction of demographic data** on the results of **DOAC Dipstick, DOASENSE Reader and LC-MS/MS** (demographic data, creatinine)
- X. Analysis **dose, last intake and duration of treatment** with each DOAC on **qualitative** results of **DOAC Dipstick** and **DOASENSE Reader** and **quantitative** results of **LC-MS/MS**
- XI. Results of DOAC Dipstick and Doasense Reader are compared between Rivaroxaban, Apixaban and Edoxaban using of LC-MSMS because DOAC Dipstick and Doasense Reader do not differentiate between the 3 direct oral factor Xa inhibitors.

9.2.2. Creatinine

- XII. Comparison of **quantitative creatinine** of Limbach (Jaffe Method) with **qualitative** results of **DOASENSE Reader**. A cut-off value of creatinine (g/L) needs to be determined for the colours low to normal by DOASENSE Reader. Differences between Readers needs to be analyzed.

Confidentiality Statement

This document is confidential and proprietary to Sponsor and HLZ Medizinische Statistik and for restricted circulation and access only. No part of it may be transmitted, reproduced, published or used by any person/s without prior written authorization.

XIII. Comparison of results of **qualitative of creatinine by DOAC Dipstick** with **qualitative results of DOASENSE Reader**. Analysis of normal ranges of the **quantitative** results of **Urine Colour Pad of DOASENSE Reader**.

9.2.3. Urine Color

XIV. Analysis of normal ranges of the **quantitative** results of **Urine Colour Pad of DOASENSE Reader**.

XV. Analysis of an interaction of the **qualitative results** of the pad **Urine Colour** on the results of the qualitative results of the pads of Factor Xa inhibitor, thrombin inhibitor and creatinine of **DOAC Dipstick** with the qualitative results **DOASENSE Reader**.

9.2.4. Other

XVI. Analysis of the results of **DOASENSE control urines** over time and influence on results of DOAC Dipstick and DOASENSE Reader.

XVII. Descriptive analysis of **Drop-out** patients (case reports)

XVIII. Analysis of the results of the **questionnaire** and interaction on results of **DOAC Dipstick**. Center effects need to be analysed.

Additional statistical evaluations may be required during analysis due to the complexity of data.

10. STATISTICAL METHODOLOGY

10.1 Statistical and Analytical Issues

10.1.1 Data management

All study practices and statistical methods are based on the International Conference on Harmonization (IHC) document “Statistical Principles for Clinical Trials.”

Confidentiality Statement

This document is confidential and proprietary to Sponsor and HLZ Medizinische Statistik and for restricted circulation and access only. No part of it may be transmitted, reproduced, published or used by any person/s without prior written authorization.

Sponsor Name: DOASENSE GmbH
Statistical Analysis Plan (SAP)
Version No.: 3 Date: 2019-05-15

Sponsor Study No.: DOA-CS-002
ClinicalTrials.gov ID: NCT03182829
HLZ Medizinische Statistik Study No.: 1-2019

A database containing patient IDs and codified numbers will be restricted to the office of [name], Department of Biometry and Statistics, Medical Faculty Mannheim. This is a locked office, and the data will only be accessible to the investigators named on this application. This database will contain patient IDs, and info on disease status, treatment/control, follow up visits, and sample analysis – only info pertinent to the outcome measures. All sample data will be assessed using codified descriptors and will contain no patient ID info. Once the LC-MS/MS data has been analyzed, unmasking treatment and control groups will be conducted at the office of [name], by the named investigators. Any publications of study results will be completed devoid of any information that could be used to identify patients included in the study. Treatment groups will summarize data. Baseline characteristics, and safety outputs total overall columns will be included to summarize all subjects.

10.1.2 Subject disposition – Descriptive Statistics

The subject disposition table will summarize the following and will be presented for all subjects by treatment group and overall.

- The number (%) of subjects entered into the study after Baseline visit
- The number (%) of subjects withdrawn before treatment completion
- The number (%) of subjects after treatment completion
- The number (%) of subjects who complete the study according study protocol

The number (%) of subjects who complete and withdraw from the study and the primary reason for withdrawal will be summarized by treatment group and overall for all subjects.

Confidentiality Statement

This document is confidential and proprietary to Sponsor and HLZ Medizinische Statistik and for restricted circulation and access only. No part of it may be transmitted, reproduced, published or used by any person/s without prior written authorization.

